5 ELIGIBILITY CRITERIA

The study population will consist of adult PLWHIV with and without COVID-19 disease and followed up at the study sites for routine clinical care. In addition, data from adult COVID-19 patients without HIV infection will be used as controls.

Cases (PLWHIV + COVID-19) will be at least 18 years of age with documented HIV-1 infection and confirmed SARS-CoV-2 infection by documented, or patient-reported, positive result on PCR testing of a nasopharyngeal or respiratory sample, before 1st April 2021.

Controls (COVID-19) will be at least 18 years of age without documented HIV-1 infection but confirmed SARS-CoV-2 infection by documented, or patient-reported, positive result on PCR testing of a nasopharyngeal or respiratory sample, before 1st April 2021.

The second control group (PLWHIV) will include individuals at least 18 years of age with documented HIV-1 infection.

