4.1 Study Schema

[figure not shown]

Figure 1: Study design with cases (PLWHIV & COVID-19) and two matched control groups.

In total, 500 cases and up to 2500 controls will be analysed.

Only real-world retrospective data will be used for this study. Deidentified retrospective data will be transcribed into the eCRF system from source data at each clinical site or from existing COVID-19 cohort databases, where appropriate.

For comparing PLWHIV & COVID-19 versus HIV seronegative COVID-19 patients, a 1:1 and 1:3 matching will be performed according to the following criteria:

- Age (+/- 5 years)
- Sex
- Ethnicity (where available)
- Month of COVID-19 diagnosis (+/- 2 months)
- COVID-19 diagnosis inpatient, 1:1 matching
OR
- COVID-19 diagnosis outpatient (ambulatory), 1:3 matching

For comparing PLWHIV & COVID-19 versus PLWHIV without COVID-19, a 1:2 matching for similar risk of acquiring COVID-19 will be performed according to the following criteria:

- Age (+/- 5 years)
- Sex
- Ethnicity (where available)

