5.1 Inclusion Criteria

- Cases (PLWHIV + COVID-19)
 - Any gender
 - At least 18 years of age
 - Documented HIV-1 infection
 - Confirmed SARS-CoV-2 infection by documented, or patient-reported, positive result on PCR testing of a nasopharyngeal or respiratory sample, before 1st April 2021

Each case should be matched to a control (1:1 or 1:3 respectively for COVID-19 controls and 1:2 for PLWHIV controls) according to the matching criteria set out in section 4.1.

- Controls (COVID-19)
 - Any gender
 - At least 18 years of age
 - No documented HIV-1 infection
 - Confirmed SARS-CoV-2 infection by documented, or patient-reported, positive result on PCR testing of a nasopharyngeal or respiratory sample, before 1st April 2021
 - Meet the matching criteria
- Controls (PLWHIV)
 - Any gender
 - At least 18 years of age

- Documented HIV-1 infection
- No evidence of SARS-CoV-2 infection
- Meet the matching criteria

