5.2 Exclusion Criteria

- COVID-19 diagnosed based on clinical criteria

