6 STUDY PROCEDURES

6.1 Subject Identification

Most PLWHIV will be identified from sites in the NEAT ID network. PLWHIV are routinely followed-up at specialised outpatient clinics with regular follow up visits as standard of care.

Since March 2020, more than 50 European sites have registered and started to provide basic information about the number of PLWHIV with COVID-19 and disease outcomes at their centres (<https://www.NEAT-ID.org/>). The dashboard provides a first estimate about the total numbers of PLWHIV with COVID-19 and where these patients are in continued care. As of 26th April 2021, 1,187 PLWHIV with COVID-19 were reported in care across Europe, with 436 hospitalisations and 78 deaths from an estimated number of 85,279 PLWHIV in routine care at these sites. These case numbers strongly suggest feasibility to recruit sufficient numbers of PLWHIV with COVID-19 and that patients have been identified at their centres already.

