- Drug treatment for COVID-19 (glucocorticoids, azithromycin, remdesivir, monoclonal antibodies against SARS-CoV2, convalescent plasma, anti-IL1 inhibitors, anti-IL6 inhibitors, lopinavir/ritonavir, and others)

For PLWHIV the following information will be collected:

- Date of HIV diagnosis
- Current ART
- CDC disease stage
- CD4 cell nadir
- Last CD4 cell count (including CD4% and CD4/CD8 ratio) and HIV-RNA before COVID-19 diagnosis, or most recent for HIV-only controls

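### HIV need not be diagnosed before COVID-19 for a case to qualify, so HIV testing prompted by severe illness can bias the primary comparison; the direction is probably upward and the size is unknown

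*Combined protocol and SAP*

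**What the plan says.** Section 5 gives the case definition: "Cases (PLWHIV + COVID-19) will be at least 18 years of age with documented HIV-1 infection and confirmed SARS-CoV-2 infection". Sections 5 and 5.1 require the SARS-CoV-2 PCR to be positive before 1 April 2021. Neither sets a date for the HIV diagnosis, in absolute terms or relative to the PCR.

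The HIV-seronegative COVID-19 controls are defined in section 5.1 by absence of a record, "No documented HIV-1 infection". No negative HIV test is required. The only exclusion, in section 5.2, is "COVID-19 diagnosed based on clinical criteria".

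Four other statements bear on the point:
- Section 5 describes the population as "adult PLWHIV with and without COVID-19 disease and followed up at the study sites for routine clinical care".
- Section 6.1 says "Most PLWHIV will be identified from sites in the NEAT ID network".
- Section 4.1 matches COVID-19 controls on care setting at diagnosis: "COVID-19 diagnosis inpatient, 1:1 matching", and 1:3 for outpatients.
- Section 6.2 collects the PCR date, the "Date of HIV diagnosis", and "Last CD4 cell count (including CD4% and CD4/CD8 ratio) and HIV-RNA before COVID-19 diagnosis".

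Section 7.3.2 estimates the effect of HIV on the composite endpoint with unadjusted and adjusted Cox models. It contains no restriction or sensitivity analysis on when HIV was diagnosed. Section 7.5 imputes missing values by chained equations and excludes variables with more than 15% missing.

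**The concern.** In a retrospective comparison, exposure should be settled before the outcome can influence it. Here it need not be. Severe illness can prompt an HIV test, and a positive result during the admission then satisfies the case definition. A mildly ill person with undiagnosed HIV is not tested, does not become a case, and may be selected as an HIV-seronegative control. These patients do have HIV, so the exposure is not false. The problem is that the chance of its being recorded depends on how ill the patient became.

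The first primary analysis is the one most affected. If severity-driven testing dominates, the bias runs in the direction of the section 3 hypothesis that HIV worsens COVID-19 outcomes.

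The second primary analysis, of factors within the PLWHIV group, is touched as well. A person diagnosed with HIV at or after COVID-19 has no CD4 count or HIV-RNA from before it. Provided overall missingness in those variables is 15% or less, section 7.5 would fill the gaps from a model informed largely by people already in care. Time since HIV diagnosis, another listed factor, would be zero or negative for such a person.

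**Working it through.** **Plan's own figures.** Section 7.1 gives control proportions of 35% hospitalised, 15% in ICU, 8% ventilated and 11% dead, and powers 500 cases against 1,500 controls at two-sided 0.05. Freedman's log-rank formula is power = Φ(√(E·k)·|1−HR|/(1+k·HR) − 1.96), with k = 500/1,500, case risk p1 = 1−(1−p)^HR and E = 500·p1 + 1,500·p. For ICU at HR 1.4, p1 = 20.35% and E = 326.7, giving Φ(2.846 − 1.96) = 81.2%. The corresponding results for hospitalisation (HR 1.3), ventilation (HR 1.6) and death (HR 1.5) are 90.8%, 86.2% and 85.4%. Table 1 states 81%, 90%, 86% and 85%. The power figures reproduce and are not in question.

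**Assumptions for the illustration** (none is stated in the documents except the 15% and 35%):
- The true hazard ratio is 1.0.
- The event risk is 15%, the ICU figure standing in for the composite.
- A share f of cases, 1% to 5% (5 to 25 of 500), have HIV found through the COVID-19 admission.
- Those patients have event risk q of 40% to 60%.

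**A. Matching ignored.** Case risk r = (1−f)·0.15 + f·q, and apparent HR = ln(1−r)/ln(0.85).

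**B. Within the inpatient-matched stratum.** Assume that all ICU patients are inpatients, that 35% of the other cases are inpatients, and that every admission-detected case is an inpatient at COVID-19 diagnosis. Inpatient controls then have risk 0.15/0.35 = 42.9%. Case risk in the stratum is s = [(1−f)·0.15 + f·q] / [(1−f)·0.35 + f], and apparent HR = ln(1−s)/ln(1−0.4286).

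| f, q | r (A) | HR (A) | s (B) | HR (B) |
|---|---|---|---|---|
| 1%, 40% | 15.25% | 1.02 | 0.1525/0.3565 = 42.8% | 0.997 |
| 3%, 50% | 16.05% | 1.08 | 0.1605/0.3695 = 43.4% | 1.02 |
| 5%, 40% | 16.25% | 1.09 | 0.1625/0.3825 = 42.5% | 0.99 |
| 5%, 50% | 16.75% | 1.13 | 0.1675/0.3825 = 43.8% | 1.03 |
| 5%, 60% | 17.25% | 1.17 | 0.1725/0.3825 = 45.1% | 1.07 |

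The range is 1.02 to 1.17 in A and 0.99 to 1.07 in B. The contrast arises because an assumed risk of 40-60% is high against all COVID-19 patients but close to the 42.9% implied for inpatients. When q is below 42.9%, the apparent HR in B falls below 1. The smallest effect that section 7.1 anticipates is 1.1. No row of B reaches it, while some rows of A exceed it.

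**What B leaves out.** Setting is matched as it stood at COVID-19 diagnosis. A person PCR-positive as an outpatient, later admitted and then found to have HIV, is compared with outpatient controls, so matching does not absorb that person's excess risk. Among inpatients, the sicker may still be tested more often. B also presumes that the comparison is made within setting. Section 7.3.2 specifies a matched analysis only for the conditional logistic models, and inpatient status is not in the Cox adjustment list.

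**The case against.** The strongest reply is that the plan already limits these cases. Section 5 describes PLWHIV in routine follow-up at the study sites, and section 6.1 draws most of them from a network of clinics with regular visits. Matching on setting gives an inpatient case an inpatient control. This stands in part. It makes such cases less likely and, as range B shows, shrinks their effect. It does not exclude them. The routine-care sentence sets no start date and is not repeated among the section 5.1 criteria, so a person diagnosed at admission and then linked to care fits it. Section 6.1 says most, not all.

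A reader might infer that the missing date inflates the HIV hazard ratio by a known amount, up to 1.17. The documents do not support that. They give no share of newly diagnosed cases, and 1.17 depends on ignoring the matching. The direction is not fixed either. A patient first diagnosed during a fatal admission never reaches an HIV clinic, so clinic-based sourcing could lose the worst outcomes and push the ratio down.

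Two further points stand. Late presenters are among the people whom the section 3 hypothesis on advanced immunodeficiency concerns, so removing them narrows the question. The imputation issue would touch only 5 to 25 of 500 cases on the assumed shares, and CD4 nadir and CDC stage are not tied to a date before COVID-19.

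**Conclusion.** The gap holds: no criterion requires HIV to be diagnosed before COVID-19, and no planned analysis uses the timing. Differential ascertainment of HIV is therefore possible in the first primary analysis. It is more likely to act upward than downward, but the direction is not certain and the size cannot be computed from the documents. On assumed shares of 1-5% with 40-60% event risk, the hazard ratio under a true value of 1.0 is about 0.99-1.07 within the inpatient-matched stratum and up to about 1.17 if matching is ignored. These are illustrations and not bounds. The consequence for CD4 and HIV-RNA is real but small on the same shares, and arises only if those variables stay at or below the 15% missingness limit. The point merits a change because the remedy is cheap and the plan already collects what it needs; a large bias has not been shown.

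**What to change.** In section 7.3.2, pre-specify an analysis of both primary questions restricted to cases whose HIV diagnosis date precedes the positive PCR date. Alternatively, make this the case criterion in the synopsis and sections 5 and 5.1. Under either option, report separately the number and outcomes of cases diagnosed with HIV at or after COVID-19. That count would show directly whether the concern matters in this dataset.

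The cost is a short text change and one programmed date check, with no new data collection. On the assumed shares, 5 to 25 of 500 cases leave the restricted analysis. Table 1 power is unchanged if 500 eligible cases are still enrolled. The restricted analysis answers a narrower question, about previously diagnosed HIV, and leaves out some late presenters with low CD4 counts. Keeping it as a sensitivity analysis beside the full population, and not as an eligibility rule, avoids losing those patients altogether.

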5.1 Inclusion Criteria

- Cases (PLWHIV + COVID-19)
 - Any gender
 - At least 18 years of age
 - Documented HIV-1 infection
 - Confirmed SARS-CoV-2 infection by documented, or patient-reported, positive result on PCR testing of a nasopharyngeal or respiratory sample, before 1st April 2021

Each case should be matched to a control (1:1 or 1:3 respectively for COVID-19 controls and 1:2 for PLWHIV controls) according to the matching criteria set out in section 4.1.

- Controls (COVID-19)
 - Any gender
 - At least 18 years of age
 - No documented HIV-1 infection
 - Confirmed SARS-CoV-2 infection by documented, or patient-reported, positive result on PCR testing of a nasopharyngeal or respiratory sample, before 1st April 2021
 - Meet the matching criteria
- Controls (PLWHIV)
 - Any gender
 - At least 18 years of age

- Documented HIV-1 infection
- No evidence of SARS-CoV-2 infection
- Meet the matching criteria

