3.3 Primary endpoint/outcome

1. The primary endpoint is a composite of: Critical care admission (high dependency unit or intensive care unit), mortality in hospital or palliative discharge when discharged from hospital, or mortality at 6 weeks after diagnosis of COVID-19 or at discharge from hospital (where applicable)

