6.2 Data collection

Only real-world retrospective data will be used for this study. Deidentified retrospective data will be transcribed into the eCRF system from source data at each clinical site or from existing COVID-19 cohort databases, where appropriate. No personal identifiable data will be transmitted to NEAT ID. The data elements will be transcribed from source data according to the data collection list below. Mechanisms to ensure data quality and integrity will be deployed as per applicable standard operating procedures and in line with GCP and GPP. Patients and controls will be identified and documented by participating sites, provided unbiased matching for inpatient/outpatient status at the time of COVID-19 diagnosis is ensured. Alternatively, and to avoid potential site-related bias during selection of HIV negative controls with COVID-19 diagnosed in hospital, data from matched controls will be obtained from appropriate existing COVID-19 cohort databases, e.g. LEOSS (Lean European Open Survey on SARS-CoV-2 infected patients) or ISARIC (International Severe Acute Respiratory and emerging Infection Consortium).

For all patients the following information will be collected:

- Age
- Sex
- Ethnicity (where available)
- Comorbidities (see appendix 1)
- Weight (kg) and height (m) (to calculate BMI)

For patients with COVID-19 the following information will be collected (where applicable):

- Date of positive PCR test result (documented or patient-reported)
- COVID-19 diagnosis inpatient or outpatient
- All-cause mortality in hospital, or palliative discharge, or mortality at 6 weeks after diagnosis of COVID-19 or at discharge from hospital
- Hospitalisation for COVID-19 and length of hospitalisation
- Critical care admission (high dependency unit or intensive care unit) for COVID-19 and length of stay in critical care
- Length of invasive ventilation
- Length of extracorporeal membrane oxygenation (ECMO)
- Need for kidney replacement therapy
- Inflammatory markers and blood cell counts at COVID-19 diagnosis¹ (if available):
 - Full blood cell count (Platelet count, RBC Count, WBC count (absolute), Haemoglobin, Haematocrit, MCV, MCH, Neutrophils, Lymphocytes, Monocytes, Eosinophils, and Basophils), ALT, AST, total bilirubin, urea, serum creatinine, calcium, glucose and HbA1C levels, total cholesterol, triglycerides, CRP, D-dimer, ferritin, and lactate dehydrogenase

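### Patient-reported PCR counts as confirmation, but no planned analysis would show whether survivor selection through that route distorts the HIV comparison of a composite that includes six-week death

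*Combined protocol and SAP*

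**What the plan says.** Section 5.1 gives cases and HIV-negative COVID-19 controls the same entry rule: "Confirmed SARS-CoV-2 infection by documented, or patient-reported, positive result on PCR testing", dated before 1 April 2021. The text of section 5 agrees for controls: "Controls (COVID-19) will be at least 18 years of age without documented HIV-1 infection but confirmed SARS-CoV-2 infection by documented, or patient-reported, positive result". The only exclusion, in section 5.2, is "COVID-19 diagnosed based on clinical criteria". Nothing states when a patient's report must have been made.

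Section 4.1 states "Only real-world retrospective data will be used for this study". The primary endpoint in section 3.3 combines critical care admission, in-hospital death or palliative discharge, and "mortality at 6 weeks after diagnosis of COVID-19 or at discharge from hospital (where applicable". The first analysis in section 7.3.2 compares this endpoint between the groups by Kaplan-Meier and Cox methods.

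On where patients are found, section 6.1 says "PLWHIV are routinely followed-up at specialised outpatient clinics with regular follow up visits as standard of care". No comparable visit is described for HIV-negative controls. Section 6.2 lets sites identify controls and, for those diagnosed in hospital, offers existing COVID-19 cohort databases as an alternative. The same section lists the item "Date of positive PCR test result (documented or patient-reported". The date of the report is not listed. Confirmation route appears in neither the matching criteria (4.1) nor the adjustment set (7.3.2), and no sensitivity analysis uses it.

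**The concern.** A documented PCR is on file whether the patient lived or died. A test that the clinic first hears of at a later visit is on file only if the patient survived to that visit. Someone who tested positive elsewhere and died at home leaves no such report. Where this route is used, the enrolled group is partly selected on one component of its own primary endpoint. Matching on outpatient diagnosis does not help, because the selection arises within that stratum.

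Primary objective 1 is a between-group comparison, and section 3 hypothesises harm from HIV. If the route is used unequally, part of the estimated HIV effect would reflect how infections were confirmed. Followed as written, the plan would give no sign of this.

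**Working it through.** **Timing.** Infections must predate 1 April 2021. Six weeks (42 days) from 31 March 2021 ends on 12 May 2021, and protocol version 1.0 is dated 28 June 2021 (Appendix 2). Every six-week window had closed before the protocol was issued. The dates on which patients made their reports are not given.

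**Inputs from section 7.1.** 500 cases, 1,500 controls, two-sided alpha 0.05, control risk of death p0 = 11%, hazard ratio 1.5, stated power 85% (Table 1). I use death alone because it is the component affected and section 7.1 gives a control rate for it.

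**Reproducing the plan's figure.** The case risk is p1 = 1 - (1 - 0.11)^1.5 = 16.0%. Expected deaths are E = 500 × 0.1604 + 1,500 × 0.11 = 80.2 + 165 = 245.2. Freedman's formula with φ = 500/1,500 = 1/3 gives

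power = Φ( √(Eφ) × (HR - 1)/(1 + φHR) - 1.96 ) = Φ( 9.04 × 0.5/1.5 - 1.96 ) = Φ(1.05) = 85.4%,

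which agrees with the stated 85%.

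**Bias model (my assumption).** A share m of infected people in a group can be found only by self-report. They have the same true risk p as the others, and they enter only if alive. Then

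observed risk = (1 - m)p / (1 - mp), and observed HR = ln(1 - observed p1) / ln(1 - observed p0).

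Example with m = 20% in cases only: 0.8 × 0.1604 / (1 - 0.2 × 0.1604) = 13.3%, and ln(0.867)/ln(0.89) = 1.22.

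Results for a true hazard ratio of 1.5:

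| m, cases | m, controls | Observed risk, cases | Observed risk, controls | Observed HR | Power to show harm |
|---|---|---|---|---|---|
| 0 | 0 | 16.0% | 11.0% | 1.50 | 85.4% |
| 10% | 0 | 14.7% | 11.0% | 1.36 | 60.1% |
| 20% | 0 | 13.3% | 11.0% | 1.22 | 27.9% |
| 30% | 0 | 11.8% | 11.0% | 1.08 | 7.1% |
| 30% | 10% | 11.8% | 10.0% | 1.19 | 20.5% |
| 20% | 20% | 13.3% | 9.0% | 1.51 | 79.1% |
| 0 | 20% | 16.0% | 9.0% | 1.85 | 99.4% |

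If HIV truly has no effect, use in cases only at m = 10% to 30% gives an observed hazard ratio of 0.91 to 0.71. Equal use scales both risks by nearly the same factor, so the ratio barely moves.

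**Dilution over both strata.** Now suppose that self-report occurs only among outpatient diagnoses, that a share q of outpatient cases is self-reported with no deaths, and that a share s of case deaths arises in that stratum (s and q are assumptions). Observed case deaths fall by the factor (1 - s) + s(1 - q) = 1 - sq, so the pooled death ratio is 1.5(1 - sq). At q = 20% this is 1.5 × 0.96 = 1.44 for s = 0.2, and 1.5 × 0.90 = 1.35 for s = 0.5. The composite also counts critical care admissions, whose survivors can still report a test, so its ratio should move less again.

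**The case against.** A reader might infer that only survivors can ever report a test, and that the HIV effect is therefore biased towards no harm or protection. The documents support neither step.

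First, section 4.1 makes the data retrospective, but not necessarily the patient's report. A patient may tell the clinic during the illness and die later, and the note remains. Section 6.1 shows that sites do register deaths: 78 among 1,187 infections (6.6%). That count is not split by confirmation route or place of diagnosis, so it weakens the strong reading without removing the mechanism.

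Second, the entry rule is worded identically for both groups. The cohort databases in section 6.2 are offered for controls diagnosed in hospital, whereas self-report matters among outpatient diagnoses, so they are little evidence of imbalance there. Outpatient controls identified at sites could equally be survivors returning to care. What stands is that the protocol describes regular visits only for PLWHIV. This makes greater use in cases plausible but does not establish it.

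Third, the larger shifts in the table are one-sided extremes for death alone. Patients who deteriorate and are admitted would usually acquire a documented test, and if self-reporters are milder cases the bias is smaller.

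It is also tempting to restrict the primary comparison itself to documented PCR. That is a debatable trade-off, because it could over-represent patients tested in hospital. Delayed entry at the report date needs a date that section 6.2 does not list.

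These objections limit direction and size. They do not supply the missing check.

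**Conclusion.** The point holds in a limited form. Accepting patient-reported PCR can under-count deaths outside hospital among outpatient diagnoses, and unequal use between groups would bias the HIV hazard ratio: down if used more in PLWHIV, up if used more in controls, with almost no change if equal. The direction is unknown, and a downward bias is only the more plausible possibility.

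The size cannot be fixed from the documents, which give no share for either group. The fall from 1.5 to about 1.36 (10%) or 1.22 (20%) assumes use in cases only, no deaths among self-reporters, equal underlying risk, and death as the sole outcome. The effect on the full composite over both strata would be smaller. This is a cheap improvement and does not invalidate the design: without it, nobody could tell which row of the table applies.

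**What to change.** In section 6.2, make confirmation route (documented or patient-reported) an explicit eCRF variable and add the date of the report. Tabulate route by group and by inpatient or outpatient diagnosis.

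In section 7.3.2, keep the first primary analysis as planned and pre-specify a sensitivity analysis restricted to matched sets with documented PCR in both groups. State that the main result will be read with caution if the two hazard ratios differ materially. Under the model above, this restricted analysis recovers 16.0% against 11.0% and a hazard ratio of 1.50. If self-reporters are milder, it describes a somewhat sicker population, which is a reason to keep it as a sensitivity analysis.

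The cost is small: the route is already named beside the PCR date, so the report date is the one new data item, and there is one extra analysis with somewhat lower precision.

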Study Population & Planned Sample Size	Cases: 500 PLWHIV with COVID-19 Controls: 1,000 PLWHIV without COVID-19 & upto 1500 HIV seronegative COVID-19 patients
Eligibility Criteria	Cases: at least 18 years of age with documented HIV-1 infection and confirmed SARS-CoV-2 infection by documented, or patient-reported, positive result on PCR testing of a nasopharyngeal or respiratory sample, before 1 st April 2021. Controls: at least 18 years of age with either: documented HIV-1 infection; or confirmed SARS-CoV-2 infection by documented, or patient-reported, positive result on PCR testing of a nasopharyngeal or respiratory sample, before 1 st April 2021. Controls must also meet the matching criteria.
Indication	HIV & COVID-19
Methodology	Only real-world retrospective data will be used for this study. Deidentified retrospective data will be transcribed into the eCRF system from source data at each clinical site or from existing COVID-19 cohort databases, where appropriate. No personal identifiable data will be transmitted to NEAT ID. Each case will be matched to control as per the criteria set out below: For comparing PLWHIV & COVID-19 versus HIV seronegative COVID-19 patients, a 1:1 or 1:3 matching will be performed according to the following criteria: 
• Age (+/- 5 years)• Sex• Ethnicity (where available)• Month of COVID-19 diagnosis (+/- 2 months)• COVID-19 diagnosis inpatient, 1:1 matching OR• COVID-19 diagnosis outpatient (ambulatory), 1:3 matching For comparing PLWHIV & COVID-19 versus PLWHIV without COVID-19, a 1:2 matching for similar risk of acquiring COVID-19 will be performed according to the following criteria: 
• Age (+/- 5 years)• Sex• Ethnicity (where available)
Number of sites	Up to 30 sites

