7.3 Statistical analysis plan

The statistical hypotheses are: 1) to show whether HIV infection is associated with severe COVID-19 compared to HIV uninfected individuals; 2) and to identify factors associated with severe COVID-19 within HIV infected population. All eligible subjects with a matching individual will be included in the analysis population (full population analysis).

Time-to-event methods, including Kaplan–Meier survival curves and Cox proportional-hazards models, will be used to compare PLWHIV with COVID-19 versus HIV seronegative COVID-19 controls for the severity of COVID-19 using parameters collected and adjusted for potential confounders. Conditional logistic regression models will be used to assess factors associated with COVID-19 within the group of PLWHIV to account for the case-control matching.

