7.3.2 Primary outcome analysis

The first primary outcome analysis will be performed on PLWHIV with COVID-19 versus HIV uninfected individuals with COVID-19. The endpoint is the occurrence of critical care admission (high dependency unit or intensive care unit), mortality in hospital or palliative discharge when discharged from hospital, or mortality at 6 weeks after diagnosis of COVID-19 or at discharge from hospital (where applicable). Kaplan-Meier estimates will be used to estimate the proportion of participants with the primary endpoint events. Unadjusted and adjusted hazard ratios (HR) will be estimated using the Cox proportional hazard model to assess the impact of HIV-infection on the severity of COVID-19. The validity of the proportionality assumption will be assessed and tested. The adjusted variables will be the following (potential confounders): Age (<60 vs 60-64 vs 65-69 vs 70-74 vs ≥75 years); Sex at birth (female vs male); Obesity (BMI>30 kg/m²); and Comorbidities (see appendix 1).

The second primary outcome analysis will be performed within the group of PLWHIV (PLWHIV with COVID-19 versus PLWHIV without COVID-19). The endpoint is to assess factors associated with severe COVID-19 within the group of PLWHIV. Conditional logistic regression models will be used to account for the case-control matching. The following variables will be assessed: Age (<60 vs 60-64 vs 65-69 vs 70-74 vs ≥75 years); Sex at birth (female vs male); Obesity (BMI >30 kg/m²); Comorbidities (see appendix 1); time since HIV diagnosis (years); current ART; CDC disease stage; CD4 cell nadir; last CD4 cell count/HIV-RNA before COVID-19 diagnosis (including CD4% and CD4/CD8 ratio) at baseline. For continuous variables, the decision to treat the variable as a continuous or categorical variable (as tertile) will be based on the lowest Akaike information criterion value for the corresponding univariable conditional logistic regression analysis. Variables achieving P < 0.20 in the univariable analysis will be retained for the multivariable analysis.

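### The infection-free criterion for HIV-only controls has no date, so PLWHIV infected after the case window closes can be neither case nor control, which can bias the within-PLWHIV odds ratios

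*Combined protocol and SAP*

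**What the plan says.** Cases need a "positive result on PCR testing of a nasopharyngeal or respiratory sample, before 1st April 2021" (section 5.1). For the HIV-only controls the same list gives "No evidence of SARS-CoV-2 infection" and no reference date. The narrative in section 5 says "The second control group (PLWHIV) will include individuals at least 18 years of age with documented HIV-1 infection", again undated.

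Section 4.1 describes their selection as "a 1:2 matching for similar risk of acquiring COVID-19 will be performed according to the following criteria". The criteria are age, sex and, where available, ethnicity. Month of diagnosis is a matching criterion only for the HIV-negative controls. Section 6.2 takes the last CD4 and HIV-RNA before COVID-19 diagnosis in cases, "or most recent for HIV-only controls".

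The groups meet in the second primary analysis, "PLWHIV with COVID-19 versus PLWHIV without COVID-19" (section 7.3.2). Section 7.3 describes it thus: "Conditional logistic regression models will be used to assess factors associated with COVID-19 within the group of PLWHIV".

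**The concern.** Controls should represent the people who could have become cases. For cases arising before 1 April 2021, these are PLWHIV in care and still uninfected at that time. What happened to them afterwards should not decide whether they may be sampled.

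As written, it does. Version 1.0 is dated 28 June 2021 (Appendix 2), so data entered under the protocol are entered at least about three months after the window closes. Someone first infected in that interval cannot be a case, because the PCR date is too late. At entry there is evidence of infection, so they cannot be a control either. The control group becomes people who stayed free of recorded infection until entry, and its make-up may differ between sites that enter data at different times.

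If a factor raises the risk of later infection, this removes more exposed than unexposed people from the controls. The odds ratios for ART, CD4, CDC stage and comorbidities then mix the association with infection before the cut-off and selection on infection after it. No planned analysis separates the two.

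**Working it through.** **The plan's own figure.** The only size statement for this comparison is the rule n = 100 + 50i in section 7.1. With n = 1500, i = (1500 − 100)/50 = 28, as stated. Undated eligibility does not change this. I use 500 cases and 1,000 controls, as in the synopsis ("Controls: 1,000 PLWHIV without COVID-19").

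**Inputs**
- Infection risk by the cut-off: 1,187/85,279 = 1.39% (section 6.1, as of 26 April 2021), used as the risk in the unexposed.
- Hazard ratio of the factor for infection: 1.5, an assumption within the 2-fold range shown below.
- c, the cumulative recorded infection in the unexposed by data entry, including the first 1.39%. The documents do not give it. Assumed range: 2% to 30%.

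**Dated rule (controls uninfected at 1 April 2021)**
- Uninfected, unexposed: 1 − 0.01392 = 0.98608
- Uninfected, exposed: 0.98608^1.5 = 0.97919
- Odds ratio = (0.02081/0.01392) × (0.98608/0.97919) = 1.495 × 1.007 = 1.505

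**Undated rule.** The odds ratio is multiplied by S(unexposed)/S(exposed), where S is the proportion staying uninfected from the cut-off to data entry. With S(unexposed) = (1 − c)/0.98608 and S(exposed) = S(unexposed)^1.5, the multiplier is S(unexposed)^(−0.5).

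| c | S(unexposed) | Multiplier | Odds ratio |
|---|---|---|---|
| 2% | 0.994 | 1.003 | 1.51 |
| 3% | 0.984 | 1.008 | 1.52 |
| 10% | 0.913 | 1.047 | 1.58 |
| 20% | 0.811 | 1.110 | 1.67 |
| 30% | 0.710 | 1.187 | 1.79 |

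If the percentage is read as later infection alone, F, the short form 1.5 × (1 − F)^(−0.5) gives values within 0.01 of these (for example 1.68 at 20%). With hazard ratio 2 in both periods, 2.01 becomes 2.21 at 10%, 2.48 at 20% and 2.84 at 30%.

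**Effects that differ between periods**
- Hazard ratio 1.5 before the cut-off and 1 after: multiplier 1.00, no bias.
- Hazard ratio 1.5 before and 0.67 after: multiplier 0.93 at c = 20%, so 1.505 falls to about 1.40.
- Hazard ratio 1 before and 1.5 after: a null factor shows 1.05, 1.11 and 1.19 at 10%, 20% and 30%. With 30% exposure assumed and matching ignored, SE(log OR) = √(1/150 + 1/350 + 1/300 + 1/700) = 0.120. The rate of significant results at nominal 5% is then about 7%, 14% and 30%.

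**The case against.** The best defence is that the bias may be trivial. Exclusion needs evidence of infection, so only recorded infections count, and the one documented figure is 1.39%. If that accrued over about 13 months and continued at the same pace for 17 more, later infection would be 1.39% × 17/13 = 1.8%. The multiplier would be 0.982^(−0.5) = 1.009, and 1.505 would become 1.52. Even at 10%, the multiplier of 1.05 is small beside a 95% confidence factor of about 1.25 either way (30% exposure, unmatched approximation). This stands as a limit on size. It does not supply the missing date.

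A site could also read the criterion as applying at the time of the matched case. It could, but nothing says so, and sites might then apply different rules.

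A reader might infer more than the documents support:
- *That the synopsis and section 5 leave this group without any infection condition.* The synopsis describes them as without COVID-19 in its sample-size and matching text, and section 5 opens by naming PLWHIV with and without the disease. Only the synopsis eligibility row and one sentence of section 5 omit it.
- *That no care requirement exists.* Section 5 places the study population in routine follow-up at the sites. What is missing is the time at which a control must have been in care.
- *That HIV-only controls were still being entered 17 months after the cut-off.* The draft amendment of 29 August 2022 concerns the COVID-19-only controls. No abstraction date is given for the HIV-only group.

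**Conclusion.** The point holds as a defect in a stated selection rule: cases have a dated infection window, and their HIV-only controls have an undated infection-free condition and no index date. Applied literally, the rule selects controls on events after the case window.

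The consequence is conditional. It is negligible if only 2 to 3% have a recorded infection by data entry and becomes material from roughly 20%. These percentages are assumptions, and the documents cannot settle which applies. It is tempting to say that the odds ratios are always inflated. That needs a factor to act alike before and after April 2021; otherwise the bias may be absent or run towards, or past, 1.

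The scope is the infected-versus-uninfected conditional logistic model in sections 7.3 and 7.3.2. The comparison with HIV-negative patients and the power figures in Table 1 are not affected.

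**What to change.** In the synopsis eligibility row and sections 5 and 5.1, define an HIV-only control as a person who:
- has documented HIV-1 infection;
- was in care at the site at the matched case's PCR date, which becomes the control's index date;
- has no evidence of SARS-CoV-2 infection before 1 April 2021, with later infection not a reason for exclusion.

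Using 1 April 2021 for infection status, not the case's own PCR date, prevents one person from serving as both case and control. The price is small at the documented incidence: 1.505 against a hazard ratio of 1.5 in the working above.

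Section 6.2 must change at the same time. Otherwise a newly admitted control's most recent CD4 or HIV-RNA could have been measured during or after their own COVID-19, and history of pneumonia (Appendix 1) could record that episode. Take controls' CD4, HIV-RNA, ART, CDC stage and comorbidities as last recorded before the index date. The same date should govern ART, CDC stage and comorbidities in the matched case, so that both sides are measured alike.

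Cost: aligned wording, one index-date field in the eCRF, and a re-check of controls already entered for care status and covariate dates. Some may need replacing. Against that, people infected later become available as controls.
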